### 5.5.2 Adverse Event (AE)

An adverse event (AE): any untoward medical occurrence in a patient or clinical trial subject administered a medicinal product and which does not necessarily have a causal relationship with this treatment. An adverse event (AE) can therefore be any unfavourable and unintended sign (including an abnormal laboratory finding), symptom, or disease temporally associated with the use of a medicinal (investigational) product, whether or not related to the medicinal (investigational) product.

In this protocol the follow AEs (not related to the IMP) are expected:

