**AEs related to lumbar puncture and injection procedure:**

Lumbar puncture: is a minimally invasive, diagnostic or therapeutic procedure that involves the removal of a small amount of cerebrospinal fluid (CSF) - the fluid that surrounds the brain and spinal cord - followed by the injection of neural cells into the lumbar region of the spinal column. In this study, the quantity of collected CSF will be replaced by the same amount of cell culture medium.

The most frequent adverse events related to this procedure is the orthostatic headache and/or back pain. The frequency of these events is about 15-30%. Normally they resolve in few days and they can be treated with bed rest, anti-inflammatory drugs and hydration. The injection of any substance in the spinal canal could induce an inflammatory/irritative reaction with highly variable severity and duration of the AE. This kind of reaction is unpredictable.

Overall, rare adverse events (<1%) are related to the simple Lumbar Puncture Procedure and consist in: risk of infection; risk of bleeding (epidural or subdural hematoma); risk of cranial nerve palsy and cauda equina syndrome; hypotension, bradycardia with or without syncope.

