**Infective Complication due to Immunosuppressive treatments**

To address the risk of opportunistic infections and organ toxicity due to combined steroid and tacrolimus treatment, periodic clinical, biochemical (full blood count, renal and liver function) drug level (FK506), immunological and virological monitoring (PCR for cytomegalovirus-CMV and Epstein virus-EBV) will be instituted at fixed intervals (see details in the specific chapter) and depending on patient's clinical and biochemical condition and previous findings, for the entire duration of the immunosuppressive treatment.

Pre-emptive CMV reactivation will be treated by standard treatment for immunosuppressed patients (i.e. ganciclovir or foscarnet). Immunosuppression reduction or discontinuation can be considered depending on severity.

EBV reactivation will be treated with immunosuppressive drug reduction or discontinuation and/or anti-CD20 (Rituximab) depending on the copy level and patient's clinical condition.

Recurrent episodes of CMV reactivation will be addressed with reduction of the immunosuppressive drug tacrolimus. Immunosuppression discontinuation will be considered depending on severity.

Bacterial infection will be treated according to standards. Repeated infections will be addressed by reduction or discontinuation of immunosuppression depending on site of infection, severity and patient's condition.

The safety profile related to concomitant medication will be assessed through general physical examination, neurological visit and through blood examination specifically hematology and chemistry parameters. At every visit signs and symptoms of possible infective events will be recorded.

For all the concomitant medication and procedure used in the protocol only AEs exceeding the grade 3 of severity according to the international definition of AEs will be reported (see also CTCAE).

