**5.5.2.1 Documentation of (serious) AE**

Between screening and last follow-up visit the patient will be asked and examined by the investigator for the occurrence of AEs. All AEs will be documented using CTCAE terms (see Appendix), including

- Severity (listed under)
- Onset date
- Stop date
- Causality assessment with study drug
- Action taken
- Outcome

The severity of AEs is defined as (see also CTCAE):

- Grade 1 mild
- Grade 2 moderate
- Grade 3 severe
- Grade 4 life-threatening
- Grade 5 death

All clearly related signs, symptoms and abnormal diagnostic procedures should be grouped together and recorded as a single term in the CRF.

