### 5.5.3.1 Attribution Definitions

**Not related:** An adverse event that is not related to the use of the investigational product.

**Doubtful:** An AE for which an alternative explanation is more likely, e.g., concomitant drug(s), concomitant disease(s), or the relationship in time suggests that a causal relationship is unlikely.

**Possible:** An AE that might be due to the use of the investigational product. An alternative explanation, e.g., concomitant drug(s), concomitant disease(s), is inconclusive. The relationship in time is reasonable; therefore, the causal relationship cannot be excluded.

**Probable:** An AE that might be due to the use of the investigational product. The relationship in time is suggestive (e.g., confirmed by de-challenge). An alternative explanation is less likely, e.g., concomitant drug(s), concomitant disease(s).

**Very likely:** An AE that is listed as a possible adverse event reaction, and cannot be reasonably explained by an alternative explanation, e.g., concomitant investigational drug(s), concomitant disease(s). The relationship in time is very suggestive (e.g., it is confirmed by de-challenge and re-challenge).

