### 5.5.6 Suspected unexpected serious adverse reaction (SUSAR)

SUSAR: an adverse event assessed as serious and unexpected and for which there is a reasonable suspected causal relationship with an investigational medical product.

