## 7 Treatment Plan

### 7.1 Experimental Treatment/Drug

The protocol will consist of a total of four treatment cohorts (TC), labeled from A to D, each of which receiving a single escalating dose of allogeneic hNPCs injected intrathecally, as it follows:

- TC-A:  $0.7 \times 10^6 \pm 10\%$  cells/kg of body weight;
- TC-B:  $1.4 \times 10^6 \pm 10\%$  cells/kg of body weight;
- TC-C:  $2.8 \times 10^6 \pm 10\%$  cells/kg of body weight;
- TC-D:  $5.7 \times 10^6 \pm 10\%$  cells/kg of body weight.

The intrathecal injection of hNPCs will be performed in a hospitalized setting.

The patients will be left in Trendelenburg position for about 30 minutes and monitored for at least 24 hours. All patients will receive normal saline solution (500 cc).

Body temperature, blood pressure, heart rate and oxygen saturation will be measured at baseline and after 15, 60, 180 minutes and then before discharge. Any toxicity will be treated at the discretion of the attending neurologist.

All patients will receive an i.v. dose of **methylprednisolone** (125 mg) immediately prior to lumbar puncture.

The injections of cells will be performed with lumbar puncture in lateral decubitus position removing about 10 cc of CSF that will be used for chemical-physical, infectivological analysis and OBs/ BBB analysis. 2 CSF ml will be stored for further research analysis. CSF will be replaced with the 10 cc of suspension solution containing hNPCs (at 2 ml/min injection rate). The injection of stem cell will be performed in about 5 minutes. In case of traumatic lumbar puncture with haematic CSF, the injection of hNPCs will not be performed. A second attempt will be performed after  $15 \pm 3$  days.

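### Section 5.5.2 lists reactions to the injected substance as expected and unrelated to the product, which contradicts the protocol's own adverse-reaction rule

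*Combined protocol and SAP*

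**What the plan says.** Section 5.5.2 introduces its lists with "In this protocol the follow AEs (not related to the IMP) are expected". Lists follow for tacrolimus, for steroids, and for lumbar puncture together with the injection procedure. The third describes the procedure as removing CSF and then injecting neural cells. It gives headache or back pain at about 15-30% and rare complications of the puncture itself below 1%. Between these it states: "The injection of any substance in the spinal canal could induce an inflammatory/irritative reaction with highly variable severity and duration of the AE". It adds: "This kind of reaction is unpredictable". Section 7.1 shows what the substance is: "CSF will be replaced with the 10 cc of suspension solution containing hNPCs".

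The closing part of 5.5.2 says that for concomitant medication and procedures "only AEs exceeding the grade 3 of severity according to the international definition of AEs will be reported".

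Other sections set different rules. Section 5.5.2.1 requires, for every event, "Causality assessment with study drug". Section 5.5.3 treats an event as an ADR when a causal relationship to the product cannot be excluded. Section 5.5.5 judges unexpectedness against the product information. Section 5.5.6 defines a SUSAR as "an adverse event assessed as serious and unexpected and for which there is a reasonable suspected causal relationship with an investigational medical product". Section 5.5.7 has all events entered in the CRF whatever their relationship or expectedness, and requires a yearly list of suspected serious ADRs.

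In 7.10, a dose-limiting toxicity (DLT) is a grade 3 event possibly related either to the cells or to the procedure. Ad hoc board review is tied to events of grade 3 or above judged possibly related to the cells. The board also reviews all safety data before each move to a higher cohort.

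**The concern.** The needle and the cells are given in one act, so an inflammatory reaction afterwards can seldom be assigned to the puncture alone. Section 5.5.2 nevertheless settles the matter before any case is seen: a reaction to the injectate is listed as expected and unrelated to the product. The same list can separate the two sources, because it ties its rare complications to the simple puncture.

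Safety is the primary objective, the trial is uncontrolled, and 5.5.1 calls the safety profile of the cells unknown. The volume is the same at every dose while the number of cells rises. A reaction to the cells might therefore rise with dose, whereas a complication of the puncture alone would not be expected to. Merging the two under a procedural label makes such a pattern harder to see. What is at stake is the ADR and SUSAR classification, the annual list, the reporting of lower-grade events, and the speed with which the board is told.

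**Working it through.** **Plan figures.** The only design figure is the maximum sample size: 4 cohorts × 6 = 24, as stated. The minimum path is 4 × 3 = 12. Section 11 is descriptive and defers the detailed analysis plan, so there is no power calculation to reproduce and no table of related events is defined.

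**The classification rules, side by side.**

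- *Causality.* Under 5.5.3 the test is whether a link can be excluded. For a reaction to a suspension that contains the product it generally cannot be, so the event would be an ADR. Under the opening line of 5.5.2 the same event is unrelated. Both cannot apply.
- *Expectedness.* Section 5.5.5 uses the product information and not the 5.5.2 list, so the word expected in 5.5.2 has no formal force. But 5.5.5 applies only to events already accepted as reactions, and 5.5.6 needs suspected causality as well as unexpectedness. If causality is denied, the expectedness test is never reached.
- *Annual list.* It contains suspected serious ADRs (5.5.7), so it depends on the same causality judgement.
- *Reporting.* Section 5.5.2 limits reporting of procedural events to those above grade 3, and Table 2 names only the patient's chart for non-serious events. Section 5.5.7 puts every event in the CRF. A grade 1 to 3 reaction labelled procedural falls between these rules. So does a grade 3 event, the level at which 7.10 defines a DLT.
- *Board review.* A grade 3 reaction assigned only to the procedure is a DLT in 7.10 but does not meet the ad hoc trigger. If it occurs in the first patient of a cohort, the cohort extends to six, and up to 6 − 1 = 5 further patients could be treated before the guaranteed review at the shift. Four cohorts give three shifts, so no shift follows cohort D.

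**Dose escalation.** Let p be an assumed probability of a grade 3 reaction per patient; the documents give none. A cohort passes with 0 of 3 DLTs, or with 1 of 3 and then 0 of 3:

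P(pass) = (1−p)³ + 3p(1−p)²(1−p)³ = (1−p)³ + 3p(1−p)⁵

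P(at least one in n patients) = 1 − (1−p)ⁿ

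| assumed p | P(pass one cohort) | at least one in 12 | at least one in 24 |
|---|---|---|---|
| 5% | 97% | 46% | 71% |
| 10% | 91% | 72% | 92% |
| 20% | 71% | 93% | 99.5% |
| 30% | 49% | 99% | about 100% |

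For p = 10%: 0.9³ + 3 × 0.1 × 0.9⁵ = 0.729 + 0.177 = 0.906. Attribution does not enter the formula, because 7.10 counts events of either origin. The label therefore leaves the escalation probabilities unchanged.

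**Dose contrast.** With 10 mL at every dose, cell concentration for a given body weight rises by 5.7/0.7 = 8.1 from cohort A to cohort D. This shows why a display by cohort is informative. It is not evidence that reactions will rise.

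**The case against.** The strongest reply is that the list overrides nothing. The parenthesis can be read as describing its scope, background events from sources other than the product, with the sentence on injected substances as general risk information. Causality is still assessed for each event, all events are still recorded, and expectedness still rests on the product information. Acute injection toxicity within three hours, including fever, is monitored separately under 5.5.1. Reporting and recording may also be meant as different acts.

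Much of this stands, and it rules out several stronger inferences:

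- *That these reactions drop out of the safety results.* This is a risk if the heading is followed, not a rule. The primary endpoint is overall safety by recording of adverse events, whatever the attribution. Treatment-related mortality is defined through the procedure, so a procedural label would not remove a death from it.
- *That dose escalation is compromised.* DLT counting includes procedural events, and the headache exception does not apply when there are meningeal signs.
- *That this is the likeliest reaction to the cells.* The profile is called unknown, the reaction unpredictable, and no rate is given.
- *That SUSARs would be lost.* The investigator's brochure is not among the documents, so whether it lists the reaction is unknown.
- *That the attribution scale blocks a finding of relatedness.* The top grade is "An AE that is listed as a possible adverse event reaction, and cannot be reasonably explained by an alternative explanation", which suits an unknown profile poorly. But de-challenge and re-challenge are only examples there, and Possible or Probable already meets the test in 5.5.3.

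What does not stand is that the safeguards remove the contradiction. Investigators would judge each event with a protocol list that already names this reaction as unrelated, and nothing says which section prevails.

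**Conclusion.** The concern holds as an internal contradiction that puts safety attribution at risk. Section 5.5.2 pre-labels a reaction to the injected suspension as unrelated to the product, against 5.5.3 and 5.5.2.1. If followed, the label could affect ADR and SUSAR classification, the annual list, reporting at grades 1 to 3, and ad hoc board review. It does not affect DLT counting or the board review before each cohort shift.

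The size cannot be given as a number of events, because the documents give no rate and define no related-event table. The conclusion rests on the texts alone and on one condition: that some investigators would take the list at its word. The probabilities shown use assumed rates and serve only to show that escalation is unaffected.

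**What to change.** - In 5.5.2, limit the list headed as unrelated to the product to tacrolimus, steroids and complications of the lumbar puncture needle alone. Remove the reaction to the injected substance from it.
- State that causality for hNPCs is assessed event by event under 5.5.3, and expectedness under 5.5.5. A presumption that every such event is at least Possible is not needed, nor is a rewrite of the attribution scale.
- In the analysis plan still to be written, tabulate reactions after injection by dose cohort, whatever their attribution.
- Reconcile 5.5.2 (including its reporting limit), Table 2, 5.5.3, 5.5.7 and 7.10. In particular, resolve the mismatch between the ad hoc board trigger, which names only the cells, and the DLT definition, which also names the procedure.

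The cost is protocol wording and CRF guidance. The count of related events may become less favourable.

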#### AEs related to the use of tacrolimus:

The most common adverse events reported with use of tacrolimus are listed below.

Nervous System: very common (**frequency >10**): headache and tremors. Common (> 1:100 < 1/10): paresthesias or dysesthesias mental status changes, seizures, encephalopathy, dizziness, impaired writing, and peripheral neuropathy. Late neurotoxicity was highly associated with severe infections and multi-organ failure.

Respiratory System: common: pleural effusion, dyspnea, lung disorders, cough, pharyngitis rhinitis and sinusitis.

Renal System: very common: renal function impairment; common: renal insufficiency acute renal failure oliguria, nephrotoxicity, kidney tubular necrosis, urinary disturbances.

Psychiatric Symptoms: very common: insomnia; common: nightmares, depression, irritability, agitation, anxiety, hallucinations, abnormal dreams.

Immunologic System: Immunologic side effects have included infectious complications as a result of immunosuppression. Cytomegalovirus is the most frequently encountered viral pathogen in patients treated with tacrolimus. Bacterial infections, primarily gram-positive and gram-negative aerobes, and fungal infections are also encountered. Progressive multifocal leukoencephalopathy (PML) related to a JC virus infections have been reported.

Hematologic System: common: anemia, leukopenia, leukocytosis, thrombocytopenia hematocrit alterations.

Cardiovascular system: very common: hypertension; common: tachycardia hemorrhage, myocardial infarction, thrombosis, hypotension, phlebitis.

Gastrointestinal system: very common: diarrhea, nausea; common: elevations in liver function tests cholangitis cholestatic jaundice hepatitis gastrointestinal hemorrhage stomatitis, gastrointestinal perforation.

Metabolic adverse events: very common: hyperkalemia, hyperglycemia, diabetes mellitus; common: hypomagnesemia, hypokalemia, hyperlipidemia, acidosis, hypocalcemia, hypophosphatemia, hyponatremia, anorexia.

Oncologic adverse events: in one study of 936 transplant patients receiving tacrolimus as primary immunosuppressive therapy, post transplant lymphoproliferative disease (PTLD) occurred in 15 (1.6%) patients. Serologic evidence of Epstein-Barr virus infections was found in all 15 patients. Oncologic side effects, or the development of new malignancies, are of particular concern

in post transplant patients. Lymphoproliferative disorders are most commonly encountered. Lymphadenopathy and monoclonal and polyclonal B cell hyperplasia as well as malignant, often fatal, B cell lymphomas have been reported.

Hypersensitivity: Hypersensitivity side effects including allergic reaction have been reported infrequently.

**AEs related to chronic steroids treatment methylprednisolone and prednisone:**

Expected AEs include: systemic hypertension; glaucoma; fluid retention; hyperglycemia and diabetes; mood and emotional disorders, central obesity; osteoporosis; cataracts; increased risk of infections; suppressed adrenal gland hormone production; thin skin, easy bruising and slower wound healing.

**AEs related to lumbar puncture and injection procedure:**

Lumbar puncture: is a minimally invasive, diagnostic or therapeutic procedure that involves the removal of a small amount of cerebrospinal fluid (CSF) - the fluid that surrounds the brain and spinal cord - followed by the injection of neural cells into the lumbar region of the spinal column. In this study, the quantity of collected CSF will be replaced by the same amount of cell culture medium.

The most frequent adverse events related to this procedure is the orthostatic headache and/or back pain. The frequency of these events is about 15-30%. Normally they resolve in few days and they can be treated with bed rest, anti-inflammatory drugs and hydration. The injection of any substance in the spinal canal could induce an inflammatory/irritative reaction with highly variable severity and duration of the AE. This kind of reaction is unpredictable.

Overall, rare adverse events (<1%) are related to the simple Lumbar Puncture Procedure and consist in: risk of infection; risk of bleeding (epidural or subdural hematoma); risk of cranial nerve palsy and cauda equina syndrome; hypotension, bradycardia with or without syncope.

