	
Exclusion criteria
 
They will be excluded from the study patients:
 
 
1. with any active or chronic infection or diseases other than MS, including but not limited to infection with HIV1-2, Hepatitis B or Hepatitis C and tuberculosis or immune deficiency syndromes;
 
2. treated with any immunosuppressive therapy, including but not limited to natalizumab and fingolimod, within the 3 months prior to screening;
 
3. treated with interferon-beta or glatiramer acetate within the 30 days prior to screening;
 
4. treated with corticosteroids within the 30 days prior to screening;
 
5. if relapse occurred during the 30 days prior to screening;
 
6. with contraindications for or intolerance to any medication, treatments and procedures that will be used in the study;
 
7. pregnant or in lactation or of childbearing age who are not willing to use a contraceptive method effective* for the entire duration of the study;
 
8. who, in the opinion of the investigator, showing any condition that would preclude study participation.
 
 
* refer to guideline  http://www.hma.eu/fileadmin/dateien/Human_Medicines/01_About_HMA/Working_Groups/CTFG/2014_09_HMA_CTFG_Contraception.pdf

Sample size
	
Max 24 patients (max 6 patients for each cohort)

Accrual/duration timeline
	
Start: 2017
 
Recruitment period:
 
For each subject the study phase will be completed after 96 weeks follow up after ATIMP administration.

Statistical considerations
	
Descriptive statistics (including means, standard deviations, and medians for continuous variables and proportions for discrete variables) will be used to summarize data as appropriate. A statistical analysis plan (SAP) with detailed statistical methods and techniques used for data analysis will be prepared before conducting the analysis.

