## 5 Study design and Endpoints

### 5.1 Description of Study Design

This is a prospective, monocentric, national, therapeutic exploratory, phase I, not randomized, open label, not controlled, single dose escalation clinical trial.

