#### c) LONG TERM (day 15 - week 96)

- overall survival
- overall safety and tolerability measured by AE recording
- long term incidence of malignancies
- percentage of subjects with treatment-related mortality defined as death due to procedure and not to the course of disease
- evaluation of changes in quality of life measures
- changes in neurological conditions

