#### 7.10 Methods of assigning patients to treatment groups

The protocol will consist of a total of four TC (from A to D), each of which receiving a single escalating dose of hNPCs injected intrathecally as it follows:

- TC-A:  $0.7 \times 10^6 \pm 10\%$  cells/kg of body weight;
- TC-B:  $1.4 \times 10^6 \pm 10\%$  cells/kg of body weight;
- TC-C:  $2.8 \times 10^6 \pm 10\%$  cells/kg of body weight;
- TC-D:  $5.7 \times 10^6 \pm 10\%$  cells/kg of body weight.

The trial will start with TC-A and will go through the subsequent enrolment of patients to be included in TCs from B to D.

Each cohort will consist of three patients at minimum. However in case of safety issue the numerosity of each TC will be increased to six patients, as explained below.

We define a DLT any adverse event of grade 3 possibly related to hNPCs or to the procedure. However we will not consider a DLT a prolonged hospitalization due to post lumbar puncture headache if not associated to any meningeal sign. We will not considered DLT adverse events related to concomitant treatments (tacrolimus and steroids)

After the inclusion of the first patient of the TC we will wait at least 14 days to treat the second patient. The same interval time will be used for all the further patients within the same TC. After the inclusion of all the planned patients within a TC, we will wait at least 3 months after the inclusion of the last patient before switching to the higher TC.

In case of none DLT within the TC, we will wait at least 3 months after the inclusion of the last patient and then we will move to the higher TC.

In case of 1 DLT within the TC, the cohort will be extended to 6 patients. If another DLT will be observed, the current dosage will be considered excessive and the immediate lower dosage will be considered MTD.

The safety monitoring board will review all safety data in the case of an AE  $\geq 3$  evaluated “possibly related to hNPC” by investigators and in any case before the shifts between TCs.

This will be repeated for every TC up to the end of the study.

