### 8.3.5 Follow-up Phase

The follow-up phase will have a duration of 96 weeks. However the patients we'll be followed for the further 6 years at least.

Patients will attend control visits weekly for the first 4 weeks after hNPCs administration and then at 8 and 12 weeks. Starting from 12 weeks visits will be performed every 12 weeks. The procedures of each visit are described in details in the flow chart.

During the follow-up phase patients will receive tacrolimus, acyclovir, co-trimoxazole and folates for the entire follow-up (till week 96) and oral prednisone for 4 weeks.

The patient will undergo:

- Neurological visit with EDSS at week 4, 12, and then every scheduled visit
- T25FW, 9-HPT, SDMT at week 24, 48, 72, 96
- Haematological visit at week 4, 12, and then every scheduled visit
- General physical examination at every scheduled visit
- Record of vital signs at every scheduled visit
- AEs, SAEs record- Relapse Assessment at every scheduled visit
- Concomitant medication revision at every scheduled visit
- **Haematological blood tests comprehensive of:**

Complete blood count, extensive clinical laboratory evaluations will be performed at week 4, 12, 24, 48 and 96

Complete blood tests and biochemistry, urinalysis evaluation will be performed at week 2, 8, 36, 60, 72 and 84

Complete blood count evaluation will be performed at week 16, 20, 30, 42, 54, 66, 78 and 90

- Infectivological screening: CMV-DNA, EBV-DNA, Galactomannan detection will be performed at week 4, 12, 24, 48 and 96
- Immunological analysis: will be performed at week 4, 12, 24, 48 and 96
- Whole blood levels of tacrolimus will be obtained as reported in the specific section, in order to maintain a target of 5-10 ng/ml.
- CSF examination will be performed at week 12. During this visit the patient will be admitted to the hospital in the morning and will be discharged the day after (24 hours of observation after procedure). Complete chemico-physical evaluation, oligoclonal bands detection, CSF Cell evaluation, virological screening, ddPCR assays.
- Electrocardiogram, Chest Xray will be performed at visit week 48 e 96 and abdominal ultrasound only at visit 96
- Brain and spinal cord MRI at week 12, 24, 48 and 96
- Neurophysiological assessment (OCT, VEP, SSEP, MEP) will be performed at week 24, 48 and 96
- Administration of MsQuol54 will be performed at 12, 24, 48, 72 and 96 weeks

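### The plan leaves its only within-patient procedural reference, the cell-free week-12 lumbar puncture, unused for reading day-0 reactions; one pre-specified descriptive table would use it

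*Combined protocol and SAP*

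**What the plan says.** - Section 5.1 describes the trial as "not randomized, open label, not controlled, single dose escalation clinical trial". The synopsis gives the size as "Max 24 patients (max 6 patients for each cohort"), and section 7.10 says "Each cohort will consist of three patients at minimum".
- Section 5.5.2, on AEs of lumbar puncture and injection, says of orthostatic headache and back pain: "The frequency of these events is about 15-30" per cent. It adds: "The injection of any substance in the spinal canal could induce an inflammatory/irritative reaction with highly variable severity and duration of the AE". Section 5.5.2 introduces its whole list of expected events as not related to the investigational product.
- On day 0 patients have the puncture and cells and are "monitored for at least 24 hours" (section 7.1).
- At week 12 there is a CSF examination with no cell injection, for which "the patient will be admitted to the hospital in the morning and will be discharged the day after (24 hours of observation after procedure") (section 8.3.5). Its stated uses are CSF analyses, ddPCR and a tacrolimus level (sections 5.6 and 8.3.5).
- Week 12 lies in the long-term window of section 5.3, whose primary endpoints include "overall safety and tolerability measured by AE recording". No rule shows AEs of the week-12 puncture separately.
- Section 11 promises descriptive statistics and a later SAP. No comparison of day 0 with week 12 is mentioned.

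**The concern.** The expected background of puncture complaints is high and the cohorts are small, so some day-0 headache or back pain is likely whatever the cells do. With no control group, the short-term AE rate has nothing inside the trial to be read against. The week-12 puncture is the only occasion on which the same patients have a lumbar puncture without cells, and the observation period is of similar length.

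Individual causality assessment does not fill this gap. Sections 5.5.2.1 and 5.5.3.1 grade the relation to the study drug only and have no category for the procedure. Section 5.5.2 also places irritative reactions to injected material, which on day 0 contains the cells, among events listed in advance as unrelated to the product.

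At stake is the reading of low-grade tolerability: whether the day-0 treatment as a whole adds reactions beyond those of a plain puncture, and how much of the long-term AE summary comes from a diagnostic procedure.

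**Working it through.** **Inputs.** Rate p = 0.15 to 0.30 (section 5.5.2). Maximum size 4 cohorts × 6 = 24, which reproduces the stated maximum. Minimum 4 × 3 = 12 if all four cohorts open and none expands. The plan gives no alpha, effect size or within-patient correlation, so those below are assumptions.

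**1. Background events on one occasion.** Expected number = n × p; chance of at least one = 1 − (1 − p)^n.

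| n | Expected, p = 0.15 to 0.30 | Chance of at least one |
|---|---|---|
| 3 | 0.45 to 0.9 | 1 − 0.85³ = 39% to 1 − 0.70³ = 66% |
| 6 | 0.9 to 1.8 | 1 − 0.85⁶ = 62% to 1 − 0.70⁶ = 88% |
| 12 | 1.8 to 3.6 | 86% to 99% |
| 24 | 3.6 to 7.2 | 98% to over 99% |

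Read as day-0 figures, these assume that the quoted rate applies without any cell effect and that onset falls within the observation period. The protocol gives no onset time, only that the complaints normally resolve in a few days. Read as week-12 figures (1.8 to 3.6 of 12 patients, or 3.6 to 7.2 of 24, entering the long-term window), they assume that the rate describes a plain puncture.

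**2. Precision of a single rate.** Exact 95% intervals: 1/3 gives 1-91%, 4/24 gives 5-37%, 7/24 gives 13-51%. A day-0 rate alone says little about the cells.

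**3. What the paired contrast could show.** Take 22.5% after the plain puncture (the midpoint), independent occasions and an exact two-sided McNemar calculation at 5%. For a 40-point excess the day-0 rate is 62.5%. The chance of an event on day 0 only is 0.625 × 0.775 = 0.484, and at week 12 only 0.225 × 0.375 = 0.084. Summing over all possible numbers of discordant pairs:

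| Excess on day 0 | Power, n = 24 | Power, n = 12 |
|---|---|---|
| +20 points | 20% | 6% |
| +30 points | 44% | 15% |
| +40 points | 71% | 30% |

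With a week-12 rate of 15% or 30%, and correlation from independence to near-complete concordance, the range at +40 points is 70-96% for 24 patients and at most about 34% for 12.

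**4. Single cohorts.** Five discordant pairs all in one direction give p = 2/2⁵ = 0.063; six give 2/2⁶ = 0.031. A cohort of 3 can never reach 5%, and a cohort of 6 has about 1% power at +40 points on the assumptions of step 3. These figures show how little a test would add; they are not a reason to plan one.

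**5. Are the two occasions alike?**

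| | Day 0 | Week 12 |
|---|---|---|
| Injection | 10 cc of cell suspension (7.1) | none stated |
| Steroids | i.v. methylprednisolone (7.1, 8.3.4); oral prednisone from day −1 (8.3.3) | none stated; oral course over by then |
| Positioning, saline | both specified (7.1) | none stated |
| Observation | at least 24 h | 24 h |
| Checks after the procedure | vital signs at 15, 60 and 180 min and before discharge; neurological examination before discharge (5.5.1, 7.1) | routine visit assessments; no post-puncture schedule |
| Next visit | weeks 1 and 2 | 12 weeks later |

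Only the first 24 hours can be matched.

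**The case against.** A reader might infer that day-0 reactions cannot be divided between needle and cells because week 12 is ignored, and that using it would divide them. The documents do not support this. Day 0 differs from week 12 by the injected volume, medium, steroids, positioning and saline as well as the cells, and the order is fixed and open label. This objection stands: the contrast is plain puncture against the whole day-0 package.

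It is also fair that the 15-30% sits under a heading covering puncture and injection, and follows a description that includes injecting cells. It may not be a plain-puncture rate, so step 1 is conditional.

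A second tempting reading is that week-12 puncture events are counted against the cells. The long-term endpoint is overall safety by AE recording, each AE has an onset date, and each is rated for relation to the study drug. Nothing says such events are attributed to the cells; they are only not shown apart.

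A third is that escalation is affected. It is not: the dose-limiting toxicity rule in section 7.10 counts events possibly due to either the cells or the procedure, so it does not need the two separated.

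Finally, the SAP is still to be written, so one table not yet promised is an omission that can still be filled, not a mistake. What survives is that no other part of the plan provides a procedural reference, and this one comes with a stay already scheduled.

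**Conclusion.** The point holds as a low-cost improvement. The trial is uncontrolled, expects a substantial background of puncture complaints, and makes no use of its one cell-free puncture as a reference. Using it would let the report say, descriptively, whether the day-0 package adds reactions beyond a plain puncture. It would not show what the cells do.

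The size is modest. On assumed rates of 22.5% and independence, even a 40-point excess would be detected with about 71% power in 24 patients and 30% in 12. Reaching 24 needs every cohort to expand, and pooling mixes doses from 0.7 to 5.7 × 10⁶ cells/kg, about an eightfold range (5.7 / 0.7 = 8.1). Single cohorts are uninformative.

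The data are not yet secure either. The end of section 5.5.2 limits reporting of AEs from protocol procedures to those above grade 3, and Table 2 places non-serious AEs in the patient's chart only. Sections 5.5.2.1 and 5.5.7 have all AEs documented or recorded in the CRF. Depending on which rule is followed, low-grade headache may be captured differently on the two occasions.

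**What to change.** 1. Reconcile the end of section 5.5.2 and Table 2 with sections 5.5.2.1 and 5.5.7, so that these AEs are captured at all grades in the same way after both punctures. This needs a protocol clarification, not only SAP wording.
2. In the SAP, pre-specify one supportive table of headache, back pain, fever, meningeal signs and new neurological signs, all grades, by onset date, in the 24 hours after day 0 and after the week-12 puncture. Pair it by patient, show it by cohort and pooled, and give the paired difference with an exact interval and no test.
3. Show AEs with onset after the week-12 puncture on a separate line within the long-term summary, and keep them in the overall AE total.
4. State with the table that it compares puncture alone with the whole day-0 package (injection, medium, cells, steroids, positioning, saline), that it cannot isolate the cells, that only the first 24 hours are matched, and that the week-12 examination schedule is less fully specified.

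The cost is the clarification in step 1, a paragraph of SAP text and one table. Both hospital stays are already planned, and no visit or procedure is added.
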